
 To compare the percentage of subjects in each treatment group requiring a change in antihypertensive medications in the ABPM ITT population 	
 Difference between treatment groups in percentage of subjects requiring no change in number or dosage of antihypertensive medications Difference between treatment groups in percentage of subjects requiring an increase in number or dosage of antihypertensive medications Difference between treatment groups in percentage of subjects requiring a decrease in number or dosage of antihypertensive medications

 To characterize the dipping pattern of sleeping BP in each treatment group in the ABPM ITT and ABPM per-protocol populations 	
 24 hour BP profile as measured by ABPM, with subjects categorized according to their sleeping BP behaviors as: 
 dippers (normal) when the reduction in the average SBP during the sleeping period was >10% to 20% of mean SBP during waking hours, extreme dippers when this reduction was >20%, non-dippers when the reduction was <10%, and reverse dippers when the mean sleep SBP was higher than the awake SBP [Bakris, 2014]

 To compare the percentage of subjects that convert from non-dipper status to dipper status between treatment groups in the ABPM ITT and ABPM per-protocol populations 	
 Difference between treatment groups in percentage of subjects that convert from non-dipper status at baseline to dipper status at end of sub-study¹

 To compare the percentage of subjects that convert from dipper status to non-dipper status between treatment groups in the ABPM ITT and ABPM per-protocol populations 	
 Difference between treatment groups in percentage of subjects that convert from dipper status at baseline to non-dipper status at end of sub-study¹

 To compare the effect of treatment with daprodustat to rhEPO on heart rate by ABPM in the ABPM ITT population 	
 Change from baseline to end of sub-study¹ in 24 hour average heart rate between treatment groups as measured by ABPM relative to time since administration of medication

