12.12.3.1. ABPM Quality Control Criteria

Subjects will need to wear the ABPM device for two 24-hour sessions during the study: at a mid-week dialysis visit starting at Week -4 until 1 week prior to randomization (baseline ABPM) and then at Week 16. The ABPM device will be placed after assessments for the main study have been completed. Subjects will be expected to wear the ABPM device for 24 hours at each session. The ABPM device will measure BP and heart rate every 30 minutes during both awake and asleep hours. The times the subject awakens and goes to sleep during this 24 hour period will be recorded.

For each session the ABPM Quality Control (QC) criteria as defined in the Project Requirement Specification (PRS) for ABPM must be met. If these criteria are not met the ABPM may be repeated (see Section 12.12.3.3).

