12.12.4. Sample Size and Power Calculations

The sample size of this sub-study has been designed based on the primary sub-study objective to demonstrate superiority in average SBP change from baseline to end of sub-study between arms (daprodustat versus rhEPO), measured by ABPM over a 24 hour assessment period. Assuming a one-sided 2.5% significance level, a true standard deviation for SBP change from baseline measured by ABPM of 11 mmHg [Peixoto, 2000], and up to a 20% withdrawal rate from the sub-study, a sample size of 68 subjects per group (136 subjects in total) will provide greater than 80% power to detect a -6 mmHg difference in treatment groups (i.e., achieve superiority). Under these assumptions, superiority will be established if there is more than a 4.2 mmHg mean difference observed in favor of daprodustat.

Assuming a 40% screen failure rate for the additional ABPM entry criteria, approximately 228 subjects that are eligible for the main study will need to be screened for the sub-study in order to randomize approximately 136 subjects. See Section 9.2.3 for more information about sample size adjustments.

Unblinded ABPM data will be reviewed by the IDMC during the conduct of the trial as part of their data monitoring responsibilities. No formal interim analysis is planned.

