In order to contextualise the primary between-group comparison, a key secondary objective is to assess within-group changes from baseline over the sub-study. Assessment of within-group changes will support interpretation of the primary analysis by identifying whether there was an absence of an increase in BP in one or both treatment groups. To that end, two-sided 95% confidence intervals will be calculated for change from baseline in each ABPM parameter separately for each treatment group. For either treatment group, a lack of adverse effect on the primary endpoint of average SBP at end of sub-study will be concluded if the upper 95% confidence limit is no more than 4 mmHg. This margin was chosen as it is less than the clinically meaningful change of 5 mmHg [Whelton, 2002] and it is half the historical increase in SBP observed with rhEPO [Krapf, 2009].

The mean and two-sided 95% CI will be estimated from the primary statistical model for within treatment arm SBP change from baseline to end of sub-study.

The change from baseline 24 hour average DBP, mean arterial pressure and heart rate at end of sub-study will be assessed in a similar way as the primary, using analogous ANCOVA models with treatment and baseline as covariates.

The differences in proportion of subjects that increase/decrease their BP medication (number or dose) will be assessed using Fisher's Exact Test. The differences between treatment groups in the proportion of subjects that convert from dippers/non-dippers at baseline to non-dippers/dippers at end of sub-study will also be assessed using Fisher's Exact Test.

Plots of the mean 24 hour average values (two-sided 95% CIs) and mean changes from baseline in 24 hour average values (two-sided 95% CIs) for BP will be provided by treatment group.

Additional statistical considerations will be addressed in the RAP.

References

Agarwal R. Blood Pressure and Mortality Among Hemodialysis Patients. *Hypertension*. 2010; 55:762-768.

Peixoto AJ ,Santos SF, Mendes RB, Crowley ST, Maldonado R , Orias M, et al. Reproducibility of ambulatory blood pressure monitoring in hemodialysis patients. *Am J Kidney Dis*. 2000; 36: 983–990.

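### ABPM sub-study: dipping is compared between arms only by Fisher's exact tests on crossings of a 10% cut; a baseline-adjusted ANCOVA of the percent nocturnal fall should be added as the main analysis

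*Protocol*

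**What the plan says.** Section 12.12.2 of the protocol classes subjects by how far mean SBP falls during sleep relative to waking hours. They are "dippers (normal) when the reduction in the average SBP during the sleeping period was >10% to 20% of mean SBP during waking hours", and "non-dippers when the reduction was <10" percent, with further classes for falls above 20% and for a sleeping mean above the waking mean. The four-class pattern is only to be characterised. The between-arm dipping endpoints are two conversion percentages. One is "Difference between treatment groups in percentage of subjects that convert from non-dipper status at baseline to dipper status at end of sub-study"; the other is the reverse conversion. Both are listed for the ABPM ITT and per-protocol populations.

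Section 12.12.5 assigns the test: differences "in the proportion of subjects that convert from dippers/non-dippers at baseline to non-dippers/dippers at end of sub-study will also be assessed using" Fisher's exact test. In the same section, 24-hour average SBP is analysed by ANCOVA with treatment and baseline, and DBP, mean arterial pressure and heart rate follow "using analogous ANCOVA models with treatment and baseline as covariates".

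On data, section 12.12.3.1 states: "Subjects will need to wear the ABPM device for two 24-hour sessions during the study". Readings are taken at half-hour intervals day and night, and sleep and wake times are recorded. Section 12.12.4 assumes "up to a 20% withdrawal rate from the sub-study, a sample size of 68 subjects per group", and bases the size on 24-hour SBP only.

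**The concern.** Each subject with two valid sessions has a percent nocturnal fall at baseline and at end of sub-study. The named tests reduce each pair of values to whether a 10% line was crossed in one direction. A move from 2% to 9% counts as no change, and a move from 9.5% to 10.5% counts as a conversion. The baseline value enters only as a side of the line. The same section uses the full scale and baseline adjustment for every other ABPM parameter and gives no reason for treating dipping differently.

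At stake is how much a secondary result can tell. If treatment changed the sleep/wake contrast, the conversion tests could easily miss a change that the same recordings would show, and a non-significant result would be hard to interpret.

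**Working it through.** **1. The plan's own figure (section 12.12.4).** Inputs: difference 6 mmHg, SD 11, one-sided 2.5%, power above 80%, withdrawal 20%.
- n per arm = 2 × 11² × (1.960 + 0.842)² / 6² = 52.8, so 53; 53 / 0.8 = 66.25, so 67. The plan states 68.
- 68 × 0.8 = 54.4, so 54 evaluable per arm. Power is 80.9% (normal) or 80.2% (t).
- Smallest significant difference: 1.983 × 11 × √(2/54) = 4.20 mmHg. The plan states 4.2.

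The stated design reproduces, and 54 per arm is carried forward.

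**2. Why 6 mmHg says nothing about dipping.** If SBP falls by 6 mmHg both awake and asleep, a fall of d percent from an awake mean A becomes d × A/(A − 6), a shift of 6d/(A − 6) points. Assume A = 130 to 150 and d = 3 to 10:
- smallest: 6 × 3/144 = 0.13 points;
- largest: 6 × 10/124 = 0.48 points.

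With SD 8 and correlation 0.3 to 0.7, ANCOVA power for shifts this small is about 3 to 6% at one-sided 2.5%, close to the error rate itself. Any power comparison for dipping therefore needs its own assumed effect.

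**3. Power under an assumed dip-specific shift.** Assumptions, since the protocol gives none: percent fall bivariate normal at the two sessions; mean 3, 6 or 10%; SD 7 or 9 points; correlation ρ 0.3, 0.5 or 0.7; a constant shift in one arm. The shift is set so that ANCOVA has about 80% power:

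shift = 2.80 × SD × √(1 − ρ²) × √(2/54) × 1.01

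- SD 7, ρ 0.7: 2.80 × 7 × 0.714 × 0.192 × 1.01 = 2.7 points.
- SD 9, ρ 0.3: 2.80 × 9 × 0.954 × 0.192 × 1.01 = 4.7 points.

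The protocol does not say whether conversions are counted among all subjects or only among those who start in the relevant class, so both were simulated (18 scenarios, 2,000 trials each, two-sided 5%):

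| Analysis | All subjects | At-risk subjects only |
|---|---|---|
| ANCOVA of percent fall | 78–81% | (same) |
| Fisher, non-dipper to dipper | 15–31% | 22–39% |
| Fisher, dipper to non-dipper | 3–19% | 8–27% |
| Either Fisher test, uncorrected | 19–36% | 29–50% |

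**4. Variations (SD 8, ρ 0.5).**
- Shift giving ANCOVA about 90%: Fisher non-dipper to dipper 21–43%. About 95%: 28–53%. Both ranges span the two denominators.
- If dipper means strictly 10–20% and non-dipper strictly 0–10%, then at ANCOVA about 80% the Fisher test has 8–18%.
- For about 80% power on non-dipper to dipper conversion among baseline non-dippers, roughly 174 to 210 evaluable subjects per arm would be needed instead of 54.

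**The case against.** The strongest reply is that the conversions are themselves the stated objectives. Section 12.12.2 asks for a comparison of conversion percentages, and Fisher's exact test suits that endpoint. A mean difference in percent fall is a different endpoint. This stands in part: deleting the Fisher tests from 12.12.5 alone would leave two listed objectives without an analysis. The continuous analysis should therefore be added, with 12.12.2 amended to match. The reply does not explain why the only between-arm dipping endpoints should be threshold crossings when the underlying measure is in hand.

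Two stronger readings are tempting, and the documents support neither. A reader might apply the planning effect for 24-hour SBP, 6/11 = 0.545 SD of change, to percent fall. With SD 8 that means shifts of 3.4 to 5.2 points, against the 0.13 to 0.48 points that a uniform 6 mmHg fall would produce; no section posits so large an effect on the sleep/wake contrast. A reader might also conclude that conversion testing always loses most of the power. When ANCOVA has about 80%, each single Fisher test keeps less than half of it. At larger effects the best case keeps a little over half (53% against 95%), and so does crediting a win on either test without correction (50% against about 80%).

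It is also fair to say that these are secondary endpoints with no power claim, that no decision rule in 12.12.5 uses dipping, and that the RAP, which is not available here, could add a continuous summary. That limits the importance. It does not change the fact that the conversion tests are the only between-arm dipping tests the protocol names.

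**Conclusion.** The point holds as a worthwhile improvement to a secondary analysis. Under the assumed means, SDs and correlations, with a constant shift of about 2.7 to 4.7 points in percent fall, about 80% power by ANCOVA becomes about 15 to 39% for the better single conversion test. The figures depend on those assumptions and on a treatment effect specific to the sleep/wake contrast; if treatment moved waking and sleeping SBP equally, neither method would have appreciable power for dipping. The primary comparison of 24-hour SBP, the superiority claim and the 4 mmHg within-arm rule are unaffected.

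**What to change.** In section 12.12.5, add as the main between-arm analysis of dipping an ANCOVA of percent nocturnal SBP fall at end of sub-study, defined as (awake mean − sleep mean) / awake mean × 100. Include treatment and baseline percent fall as terms, and report the treatment difference with a two-sided 95% CI in the ABPM ITT and per-protocol populations. Add the matching endpoint to the dipping objectives in section 12.12.2. Keep the two conversion comparisons as supportive. While editing, state their denominator, the class of a fall of exactly 10%, and how extreme and reverse dippers count.

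The cost is one additional secondary model and some wording, with no new data, visits or subjects. The downside is that the main dipping result becomes a mean difference in percent fall, which is less familiar than a change of class; the retained conversion comparisons still show the latter.

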12.13.1. Rationale

The purpose of this sub-study is to collect PK samples in a subset of subjects (n=200) randomized to daprodustat in the main study to enable exploratory exposure-response and exposure-safety analyses.

12.13.2. Objectives and Endpoints

Objectives	Endpoints
Primary	

 To summarize the PK parameters of daprodustat and three major metabolites in dialysis subjects 	
 Plasma daprodustat, M2, M3, and M13 PK parameters pre-dose trough (C_{tau}) and C_{max}
Exploratory	

 Evaluate graphical relationships between exposure parameters and selected efficacy endpoints 	
 Scatter plots of daprodustat PK parameters (C_{tau} and C_{max}) dose normalized to 1 mg vs. percent time in range during EP. Scatter plots of average daprodustat dose during EP vs. percent time in range during EP. Scatter plots of daprodustat PK parameters (C_{tau} and C_{max}) dose normalized to average dose during EP vs. percent time in range during EP. Scatter plots of daprodustat PK parameters (C_{tau} and C_{max}) dose normalized to 1 mg vs. change from baseline of Hgb during EP. Scatter plots of average daprodustat dose during EP vs. change from baseline of Hgb during EP. Scatter plots of daprodustat PK parameters (C_{tau} and C_{max}) dose normalized to average dose during EP vs. change from baseline of Hgb during EP.

 The evaluate graphical relationships between daprodustat exposure and MACE and the combined safety endpoint of MACE + thromboembolic event+ hospitalization for HF 	
 Boxplots of daprodustat PK parameters (C_{tau} and C_{max}) dose normalized to 1 mg by subjects with or without MACE or combined safety endpoint. Boxplots of daprodustat PK parameters (C_{tau} and C_{max}) dose normalized to dose at time of MACE or combined safety endpoint (or end of treatment if no endpoint) by subjects with or without MACE or combined safety endpoint.

12.13.3. Study Design

This is a multicenter sub-study of daprodustat study 200807 (the main study). Approximately 200 subjects from centers in selected countries that are participating in the main study will be invited to participate in the PK sub-study.

12.13.4. Additional Inclusion Criteria

- Signed written informed consent prior to beginning sub-study-related procedures (subject must understand the aims, procedures, and possible consequences of the sub-study). Note: Consent to participate in the sub-study is separate from consent to participate in the main study.
- Subject must be receiving randomized daprodustat treatment in the main study.
- Only subject's receiving in center hemodialysis are eligible.

12.13.5. Study Assessments

Blood samples will be collected at any single study visit from the Week 4 through Week 52 visit (i.e., PK is collected at one visit only, based on convenience for the subject/site). Samples will be collected at the following times with respect to dosing of randomized treatment:

- Predose, 0.5h, 1h, 2h and 3h post dose.

On the day of the scheduled PK visit:

- The subject is to be instructed **not** to take their dose at home before the visit, but to take the dose in the clinic after the pre-dose sample is collected.
- The dose taken in the clinic **should be from the same bottle(s) the subject has been using prior to the PK visit**, not from any newly dispensed bottle(s) at the PK visit (Note: a subject placed on a dose hold at the previous visit **should not** have PK samples taken; PK collection should be delayed until the visit after the subject has restarted study treatment).
- Record the date and actual time of the dose taken in the clinic and the three doses prior to the visit, and the date and actual time of all PK samples collected. Samples may be collected within ± 20 min of the planned collected time.
- Based on the time of dosing, samples may be obtained before, during, or after any dialysis procedure. The start and stop time of the dialysis procedure will also be recorded at this visit.

Plasma PK analysis will be performed under the control of GSK PTS-DMPK/Scinovo, the details of which will be included in the SRM. Concentrations of main daprodustat and metabolites (GSK2391220 (M2), GSK2531403 (M3), and GSK2531401 (M13)) will be determined in plasma samples using the currently approved bioanalytical methodology. Raw data will be archived at the bioanalytical site.

12.13.6. Sample Size

It is estimated that 150 sub-study subjects are required to have at least 80% power that the MACE rate in the sub-study is within 20% of the MACE rate in main study. To

account for missing or non-evaluable PK samples, approximately 200 subjects will be randomized. See Section 9.2.3 for more information about sample size adjustments.

Approximately 45% (n~65) of subjects in this sub-study would be expected to meet the combined safety endpoint (and n~85 subjects would not). Based on a between subject variability (CVb%) estimate for C_{max} and C_{tau} of up to 100% (as seen in a prior Phase 1 study in CKD and from population PK analysis), 65 subjects would be sufficient to have >80% power that the 95% CI around the geometric mean is within 0.6 to 1.4 times the estimate. This is considered sufficient precision for the descriptive analysis proposed.

12.13.7. PK/PD Analyses

The 'PK Population' is defined as subjects for whom a PK sample was obtained and analyzed. This will be the population used for all the PK displays.

The following plasma PK parameters will be determined for daprodustat and metabolites: C_{tau} (pre-dose) and C_{max} .

Plasma daprodustat and metabolites concentration data will be listed and summarized by planned collection time and daprodustat dose administered at PK visit. PK parameter data will be listed and summarized by daprodustat dose administered at PK visit, and dose-normalized (per mg) PK parameter data will be summarized.

All PK data will be stored in the Archives, GlaxoSmithKline Pharmaceuticals, R & D.

Based on exploratory graphs (Section 12.13.2), and the efficacy and safety results from the main study, post-hoc exploratory exposure-response/safety modelling may be conducted, including exploratory graphics with metabolites. Further details will be provided in the RAP of the main study.

12.14. Appendix 14: Country Specific Requirements

12.14.1. French Administrative Considerations and Specifics Requirements

This appendix includes all the requirements of the French law (n° 2004-806 of 9th August 2004), and identifies, item per item, the mandatory modifications or additional information to the study protocol and includes specific GSK requirements.

1. Concerning the « STUDY POPULATION »

In line with the local regulatory requirements, the following text in section «**OTHER STUDY ELIGIBILITY CRITERIA CONSIDERATIONS** » is added: A subject will be eligible for inclusion in this study if he /she is either affiliated to or beneficiary of a social security category.

It is the investigator's responsibility to ensure and to document (in source document - patient notes) that the patient is either affiliated to or beneficiary of a social security category.

2. Concerning the “DATA ANALYSIS AND STATISTICAL CONSIDERATIONS” and specially in the “SAMPLE SIZE ASSUMPTION”

The expected number of patients to be recruited in France is declared to the French regulatory authority.

3. Concerning the “STUDY CONDUCT CONSIDERATIONS”

In section “Regulatory and Ethical Considerations, Including the Informed Consent Process”

Concerning **the process for informing the patient** or his/her legally authorized representative, the following text is added:

French Patient Informed Consent form is a document which summarizes the main features of the study and allows collection of the patient's written consent in duplicate. It also contains a reference to the authorization of L'Agence nationale de sécurité du médicament et des produits de santé (ANSM) and the approval from the French Ethics committee.

Concerning the management of the Patient Informed Consent forms, the following text is added:

The first copy of the Patient Informed Consent form is kept by the investigator. The second is given to the patient or his/her legally authorized representative

- In section concerning the “**NOTIFICATION TO THE HOSPITAL DIRECTOR**” the following text is added:

In accordance with Article L1123-13 of the Public Health Code, the Hospital Director is informed of the commitment to the trial in his establishment. The Hospital Director is supplied with the protocol and any information needed for the

financial disposition, the name of the investigator(s), the number of sites involved in his establishment and the estimated time schedule of the trial (R.1123-63).

- In section concerning the “**INFORMATION TO THE HOSPITAL PHARMACIST**” the following text is added:

In accordance with Article R.1123-64 of the Public Health Code, the Hospital Pharmacist is informed of the commitment to the trial in his establishment. The Pharmacist is supplied with a copy of the protocol (which allows him to dispense the drug(s) of the trial according to the trial methodology), all information concerning the product(s) of the trial (e.g. included in the CIB), the name of the investigator(s), the number of sites involved in his establishment and the estimated time schedule of the trial.

- In section “**DATA MANAGEMENT**” the following text is added:

Within the framework of this clinical trial, data regarding the identity of the investigators and/or co-investigators and/or the pharmacist if applicable, involved in this clinical trial, and data regarding the patients recruited in this clinical trial (patient number, treatment number, patient status with respect to the clinical trial, dates of visit, medical data) will be collected and computerized in GSK data bases by GlaxoSmithKline Laboratory or on its behalf, for reasons of follow up, clinical trial management and using the results of said clinical trial. According to the Act n° 78-17 of 6th January 1978 further modified, each of these people aforesaid has a right of access, correction and opposition on their own data through GlaxoSmithKline Laboratory (Clinical Operations Department).

4. Monitoring visits

The Health Institution and the Investigator agree to receive on a regular basis a Clinical Research Assistant of GLAXOSMITHKLINE or of a service provider designated by GLAXOSMITHKLINE. The Health Institution and the Investigator agree to be available for any phone call and to systematically answer to all correspondence regarding the Study from GLAXOSMITHKLINE or from a service provider designated by GLAXOSMITHKLINE. In addition, the Health Institution and the Investigator agree that the CRA or the service provider designated by GLAXOSMITHKLINE have direct access to all the data concerning the Study (test results, medical record, etc.). This consultation of the information by GLAXOSMITHKLINE is required to validate the data registered in the eCRF, in particular by comparing them directly to the source data. In accordance with the legal and regulatory requirements, the strictest confidentiality will be respected.

5. Data entry into the eCRF

The Health Institution and the Investigator agree to meet deadlines, terms and conditions of the Study's eCRF use here below:

The Health Institution and the Investigator undertake:

- 1) That the Investigator and the staff of the investigator center make themselves available to attend the training concerning the computer system dedicated to the eCRF of the Study provided by GLAXOSMITHKLINE or by a company designated by GLAXOSMITHKLINE.

- 2) That the Investigator and the staff of the investigator center use the IT Equipment loaned and/or the access codes only for the purpose of which they are intended and for which they have been entrusted to them, namely for the Study achievement, to the exclusion of any other use.
- 3) That the Investigator and the staff of the investigator center use the IT Equipment loaned according to the specifications and manufacturer's recommendations which will have been provided by GLAXOSMITHKLINE.
- 4) To keep the IT Equipment and/or access codes in a safe and secure place and to only authorize the use of this IT Equipment by investigator center staff designated by the principal investigator to enter the data of the Study.
- 5) That the Investigator and the staff of the investigator center enter the data of the eCRF related to a patient visit in the 3 days following the date of the patient visit or, for the patient test results, in the 3 days following the reception of the results of such tests.
- 6) That the Investigator resolves and returns to GLAXOSMITHKLINE the data queries issued by GLAXOSMITHKLINE or a service provider designated by GLAXOSMITHKLINE within 7 days after the reception of the request of clarification or in a period of one (1) day during the final stage of clarification of the data base or in such other period as provided by GLAXOSMITHKLINE and/or a company designated by GLAXOSMITHKLINE.
- 7) To be responsible for the installation and payment of the required Internet connections needed for the use of the IT Equipment, Computer systems and/or access codes.
- 8) To return at the end of the Study the IT Equipment and/or access codes to GLAXOSMITHKLINE or to any company designated by GLAXOSMITHKLINE and any training material and documentation. The IT Equipment cannot under any circumstances be kept by the Health Institution or the Investigator for any reason whatsoever.

6. CTR publication

It is expressly specified that GLAXOSMITHKLINE and/or the Sponsor can make available to the public the results of the Study by the posting of the said results on a website of the GLAXOSMITHKLINE GROUP named Clinical Trial Register (CTR) including the registration of all the clinical trials conduct by the GLAXOSMITHKLINE Group and this before or after the publication of such results by any other process.

7. Data Protection French Law of 6 January 1978 (CNIL)

In accordance with the Data Protection French Law of 6 January 1978 as modified, computer files used by GLAXOSMITHKLINE to monitor and follow the implementation and the progress of the Study are declared with the Commission Nationale de l'Informatique et des Libertés (CNIL) by GLAXOSMITHKLINE. The Investigator has regarding the processing data related to him a right of access, of rectification and of opposition with GLAXOSMITHKLINE in accordance with the legal provisions. This information can be transferred or be accessed to other entities of GLAXOSMITHKLINE Group in France, Britain or United States, what the Investigator agrees by the signature of the present Protocol.

